7.12.3 Severity of adverse events

The investigator is to classify the severity (intensity) of an AE according to the following definitions:

- Mild The subject was aware of the signs and symptoms, but the signs and symptoms were easily tolerated and does not interfere with daily activity.
- Moderate The signs and symptoms were sufficient to restrict, but did not prevent, usual daily activity for the subject. The subject is still able to function.
- Severe The subject was unable to perform usual daily activities.

The maximum severity recorded during the course of an AE (mild, moderate, or severe) will be considered the final severity.

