7.12 Adverse events

7.12.1 Adverse events assessments

The investigator or designee is responsible for obtaining, assessing, and documenting all AEs during the trial.

An AE is any untoward medical occurrence in a patient or clinical investigation subject administered an investigational or non-investigational medicinal product and which does not necessarily have to have a causal relationship with this treatment. An AE can therefore be any unfavourable and unintended sign (including an abnormal laboratory finding, for example), symptom, or disease temporally associated with the use of a medicinal product, whether or not considered related to the medicinal product.

All AEs will be documented in the eCRF, including a description of each AE, AE relationship to IMP administration, start and stop dates, seriousness, severity, action taken and outcome.

Any AE that meets the serious criteria must be reported as an SAE to PharmaLex (PLX) within 24 hours of first awareness.

Contact information:

Company: PharmaLex A/S, [name]

E-mail: [contact]

Throughout the trial, the occurrence of AEs should be monitored by nondirective questioning of the subject at each visit. Information on AEs can also be obtained from signs and symptoms detected during examinations, observations made by the trial site personnel, or spontaneous reports from subjects. Pre-existing conditions that worsen during the trial should also be recorded as AEs. This will also include worsening of the disease as judged by the investigator.

AEs requiring therapy must be treated in accordance with recognised standards of medical care to protect the health and well-being of the subject. Treatment due to an AE will be recorded in the subject's records and on the appropriate eCRF.

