7.12.2 Reporting of adverse events

Adverse event information will be collected from individual trial subjects from signature of the informed consent form until the last trial visit.

If the event is reported as an SAE, the timelines for SAE reporting apply (see Section 7.12.10). If the event is reported as non-serious AE, it should be reported on the appropriate eCRF page.

All SAEs and related non-serious AEs must be followed by the investigator until they are resolved or until judged by the investigator to be stable/needing no further follow-up. All

relevant follow-up information will be reported in the eCRF (and to PharmaLex if it qualifies as an SAE, see Section 7.12.1).

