8.7.1 Adverse events

Adverse events will be coded using Medical Dictionary for Regulatory Activities (MedDRA) terminology. Treatment-emergent adverse events (TEAEs), related TEAEs, non-serious TEAEs, serious TEAEs, related serious TEAEs, TEAEs leading to treatment discontinuation and Deaths

will be summarised by the overall incidence of at least one event, incidence by body system, and incidence by body system and preferred term. Each subject will contribute only once (e.g., the first occurrence) to each of the rates, regardless of the number of occurrences (events) the subject experiences. The number of occurrences will also be displayed.

Treatment-emergent AEs will be summarised by severity (mild, moderate, or severe), and by relationship to trial product (not related, unlikely, possibly, or probably). In summaries of severity and relationship, subjects who report more than one event that are mapped to the same preferred term will be counted only once under the strongest severity and relationship, accordingly. An AE is treatment-emergent if its date of onset is on or after the day of start of trial medication. An AE is related if relationship to trial product is not assessed as unrelated.

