5.6.4 Adverse Events

Adverse events (AE) will be coded using MedDRA version 24.1 terminology. Treatmentemergent adverse events (TEAEs) related TEAEs (unlikely related, possibly related, and probably related), non-serious TEAEs, serious TEAEs (TESAEs), related TESAEs, TEAEs leading to treatment discontinuation or trial withdrawal, and deaths will be summarized for the overall incidence of at least one event, incidence by SOC and incidence by SOC and PT.

By definition, TEAE is an AE that began after the start of trial medication treatment. TESAE's are any TEAE's that are reported as serious in the eCRF.

Each subject will contribute only once to each of the incidence rates, regardless of the number of occurrences (events) the subject experiences. The number of occurrences for each SOC and PT will also be displayed.

TEAEs will also be descriptively summarized by severity (mild, moderate or severe) and by relationship to IMP [not related or related (unlikely related, possibly related and probably related)]. In summaries of severity and relationship, subjects who report more than one event mapped to the same SOC or PT will be counted only once under the strongest severity and relationship, accordingly.

An AE is treatment-emergent if its date of onset in on or after the first application date of IMP. An AE is related if relationship to IMP is assessed as unlikely related, probably related, or possibly related.

TEAEs, TESAEs, TEAEs leading to treatment discontinuation or study withdrawal and deaths will be listed by subject.

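### Treatment-emergent status is set by onset date alone, so a screening AE that worsens or turns serious after first application is left out of the TEAE and TESAE tables and the AE listings named in the SAP

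*Protocol*

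**What the plan says.** **Collection.** Protocol 7.12.2 collects AEs "from signature of the informed consent form until the last trial visit". Protocol Table 3 allows screening from Day -28 to Day -1, so AEs with a pre-dose start date can exist.

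**Recording.** Protocol 7.12.1 states: "All AEs will be documented in the eCRF, including a description of each AE, AE relationship to IMP administration, start and stop dates". The remaining fields named there are seriousness, severity, action taken and outcome. No date of worsening, or of becoming serious, is named. On severity, Protocol 7.12.3 states: "The maximum severity recorded during the course of an AE (mild, moderate, or severe) will be considered the final severity". Protocol 7.12.4 likewise keeps one relationship per AE, the last one recorded.

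**Worsening.** The only rule is in Protocol 7.12.1: "Pre-existing conditions that worsen during the trial should also be recorded as AEs". The next sentence extends this to worsening of the disease in the investigator's judgement.

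**Treatment-emergent status.** Protocol 8.7.1 states: "An AE is treatment-emergent if its date of onset is on or after the day of start of trial medication". SAP 5.6.4 states: "By definition, TEAE is an AE that began after the start of trial medication treatment", and later in the same section restates the rule as onset on or after the date of first application. None of the three statements has a worsening clause. SAP 5.6.4 defines a TESAE as a TEAE reported as serious.

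**Outputs.** Apart from deaths, the AE tables in Protocol 8.7.1 and SAP 5.6.4 are built on TEAEs. On listings, SAP 5.6.4 states: "TEAEs, TESAEs, TEAEs leading to treatment discontinuation or study withdrawal and deaths will be listed by subject".

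**The concern.** The treatment-emergent tables are where the two arms are compared on safety. An event that was mild before dosing and becomes severe or serious under treatment is a change during exposure, yet the stated definition treats it as a pre-treatment event. The error can go only one way: on-treatment worsening is undercounted.

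Protocol 2.3 describes this as the first clinical trial of the cream and of its vehicle, with about 72 subjects on cream and 36 on vehicle. At that size a few events can alter how a safety table reads.

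The rule also treats similar cases differently. A condition present before consent that worsens on Day 5 is recorded as an AE under Protocol 7.12.1; dated at its worsening, it is a TEAE. If the same condition starts the day after consent, it is already an open AE with a pre-dose onset, and no text clearly brings its worsening into the count. Classification can then depend on the consent date instead of on exposure.

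A related difference concerns SAEs. The safety endpoints in Protocol 4.2 include SAEs with no treatment-emergent limit. SAP 3.5 reports TESAEs instead, and the list of changes in SAP 6.2 does not mention it.

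**Working it through.** No formula applies to the rule itself, so the check follows one AE through the text: complete start date on Day -10, mild, still open at first application, changed on Day 5.

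1. **Is it an AE record?** Yes, under Protocol 7.12.2. The schedule of assessments marks AEs only from Baseline, but 7.12.2 explicitly says from consent.
2. **Does the change open a new record?** No text requires one. Sections 7.12.3 and 7.12.4 assume that severity and relationship can change within an AE and reduce each to one final value.
3. **Is it treatment-emergent?** Its onset (Day -10) precedes first application, so it is not, under Protocol 8.7.1 or either statement in SAP 5.6.4.
4. **Where does it appear?**

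| What happens on Day 5 | Missing from | Still visible in |
|---|---|---|
| Becomes severe | TEAE tables, including severity and relationship; TEAE listing | All-data listings (Protocol 8.1) |
| Becomes serious | The above, plus the TESAE table and listing | All-data listings; SAE report within 24 hours (Protocol 7.12.9 and 7.12.10) |
| Leads to discontinuation | TEAE tables and listing, plus those for TEAEs leading to discontinuation or withdrawal | All-data listings; reasons for discontinuation in disposition (SAP 5.4) |
| Is fatal | TEAE and TESAE outputs | Deaths; all-data listings; SAE report |

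5. **Incomplete dates.** Under SAP 6.1 an AE is treatment-emergent if its start date is wholly missing, or if only the day is missing and the month is that of first application. An AE with no date is therefore counted, while one known to have worsened on treatment is not.

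**Scale.** The affected share is P(AE starts in screening) × P(still open at first application) × P(worsens on treatment). The documents give none of the three. Purely as assumptions, take 20–50%, 40–60% and 10–20%:

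- low: 0.2 × 0.4 × 0.1 = 0.8%, or 0.6 of 72 on cream and 0.3 of 36 on vehicle;
- high: 0.5 × 0.6 × 0.2 = 6.0%, or 4.3 of 72 and 2.2 of 36.

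This shows only that the count would be small under such values. It is not an estimate for this trial.

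**The case against.** A reader might infer that the event vanishes from the report. The documents do not support that. Protocol 8.1 promises subject listings of all collected and derived data, SAP 5.4 summarises reasons for stopping treatment, SAE reporting does not depend on onset date, and deaths are not limited to TEAEs. These outputs keep the event visible, but they do not put it back into the between-arm AE tables.

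A reader might also infer that the trial would miss its main local signal. That goes too far as well:

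- Worsening itch is worsening of the trial disease, which Protocol 7.12.1 has recorded as an AE.
- A true application-site reaction cannot start before the first application, so the onset rule catches it.
- Clinically significant abnormalities at the Screening visit become medical history (Protocol 7.4 to 7.6 and 7.8), so a later worsening falls under the pre-existing-condition rule.
- Exclusion criterion 7 removes many concurrent skin conditions.
- Skin findings are also followed through the physical examination and the CGA and CTA.

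Next, no sentence says that a worsened AE stays one record. That is inferred from the single-value rules and the absence of a splitting rule. The eCRF completion instructions are not among the documents, and a site could read pre-existing as covering anything present before dosing. This stands as a caveat. If sites may read it differently, a written rule is still needed.

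Finally, Protocol 8.7.1 itself summarises serious TEAEs, so the move from SAEs to TESAEs does not begin with the SAP. The endpoint in Protocol 4.2 and the analysis text still differ.

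**Conclusion.** The point holds as a gap in a definition, and it should be corrected. As written, an AE with a complete start date in screening that worsens, turns serious or leads to discontinuation after first application is excluded from the TEAE and TESAE tables, from the table of TEAEs leading to discontinuation, and from the listings named in SAP 5.6.4. Any bias in those counts is downward. It is not established that the event is absent from all outputs, or that local reactions to the cream would go unseen.

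The number of subjects affected cannot be computed from the documents and is probably small. The conclusion rests on two readings: that AEs are recorded from consent, as 7.12.2 says, and that a worsening stays within the existing record, which the text implies but does not state.

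**What to change.** 1. **Definition (Protocol 8.7.1 and SAP 5.6.4).** Define a TEAE as an AE with onset on or after first application, or an AE present before it that increases in severity or becomes serious on or after it. Use this one statement in SAP 5.6.4 in place of the two now there.
2. **One counting mechanism (Protocol 7.12.3 and the eCRF instructions).** When a pre-dose AE worsens or becomes serious after first application, close the pre-dose record and enter the worsening as a new AE dated when it happened, counted once. Pre-dose severity is then not attributed to treatment. A worsening clause applied to the old record as well as the new one would count the same change twice.
3. **Listings (SAP 5.6.4).** List all AEs and all SAEs with a treatment-emergent flag. This also shows a pre-dose AE that leads to discontinuation without a change in severity or seriousness, which the new definition would still leave out of the TEAE tables.
4. **SAE endpoint.** Either report all post-dose SAEs, in line with Protocol 4.2, or record the narrowing to TESAEs in SAP 6.2.

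The cost is a sentence or two in each document, an eCRF completion instruction and slightly higher TEAE counts. No efficacy analysis changes.

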7.12.4 Relationship of adverse events to trial treatment

The investigator is responsible for assessing the relationship of an AE to the IMP treatment using good clinical judgment and the following definitions:

- Not related The AE is clearly explained by another cause not related to the IMP administration; the temporal relationship of the AE to IMP administration makes a causal relationship clearly improbable or concomitant medication, therapeutics interventions, or underlying condition provide a sufficient explanation for the observed AE.
- Unlikely related The AE is most likely related to actiology other than the IMP administration; the temporal relationship of the AE to IMP administration makes a causal relationship unlikely, and other concomitant medication, therapeutic interventions or underlying disease provide plausible explanations for the observed AE.
- Possibly related The AE and administration of IMP are temporally related, but the AE can be explained equally well by causes other than the IMP administration. A causal relationship is conceivable and cannot be dismissed.
- Probably related The AE and use of IMP are temporally related, and the AE is more likely explained by IMP administration than by other causes. Good reason and sufficient documentation to assume a causal relationship.

The last relationship recorded during the course of an AE will be considered the final relationship as the investigator is assumed to have had the most information to perform the relationship assessment at that time.

7.12.5 Outcome of adverse event

The outcome of an AE will be classified as:

- Recovered/resolved
- Recovered/resolved with sequelae (note: in case of sequelae, the sequelae must be reported in eCRF)
- Recovering/resolving
- Not recovered/not resolved
- Fatal
- Unknown

7.12.6 Unexpected serious adverse events

All SAEs will be assessed for expectedness by the sponsor or designee. An SAE is considered "unexpected" if its nature or severity is not included in the "Reference safety information" section in the MC2-25 cream IB.

7.12.7 Trial medication overdose

An overdose of the IMP is a dose that is higher than the highest dose under clinical investigation.

In the event of a clinically significant overdose, as judged by the investigator, the event should be reported as an AE and supportive treatment or discontinuation of the IMP may be applied as judged by the investigator. In view of the >40-fold systemic safety margin (see Section 2.3), the administered dose may be several fold higher than the highest dose under clinical investigation without necessarily qualifying as a clinically significant overdose.

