The MC2-25 cream is not authorised in EU or in other countries outside the EU. This is the first clinical trial with MC2-25 cream and MC2-25 vehicle so no clinical data are available. As noted above, the active ingredient Ala-Gln is included in the product Dipeptiven[®], which has been approved for IV human use at doses up to 0.5 g per kg body weight per day. According to the Dipeptiven[®] SmPC (2015) there are no known undesirable effects when administered correctly. In the present trial a maximum of 50 g MC2-25 cream 3% (w/w) will be used per day, i.e., 0.5 g cream per 2% body surface area (see fingertip unit rule described above) and twice daily application. This corresponds to ~0.02 g Ala-Gln/kg/day (1.5 g Ala-Gln per day in a 70-kg adult) and a resulting safety margin of 25 compared to IV administration assuming that all topically applied Ala-Gln is absorbed into the systemic circulation. However, less than 1% of the total applied Ala-Gln dose was recovered in the receptor fluid (a surrogate for absorption into the systemic circulation) in an in vitro whole human skin penetration study with Ala-Gln cream (see IB Section 4.3.1.1, Skin penetration study using whole human skin). This corresponds to 0.0002 g Ala-Gln/kg/day and a resulting systemic safety margin of 2500. Assuming that the skin defect in CKD-aP is similar to AD skin (worst case scenario), and consequently the skin permeation is 2.5-fold higher than in healthy skin (Yoshiike 1993), then the resulting systemic safety margin would be 10 or 1000 if either all or less than 1% of topically applied Ala-Gln was absorbed, respectively. In view of the benign safety profile of Dipeptiven® and the high safety margin, the risk of treatment-related systemic adverse effects is considered to be negligible in this trial.

Ala-Gln_is rapidly split into alanine and glutamine after infusion. In man, half-lives of between 2.4 and 3.8 min (4.2 min in terminal renal insufficiency) and a plasma clearance of between 1.6 and 2.7 l/min were determined (see IB Section 4.3, Pharmacokinetics and product metabolism in animals). So, even if topical application of MC2-25 cream leads to systemic exposure to Ala-Gln, then it will rapidly be metabolized to the two respective amino acids and become part of the body's amino acid homeostasis. In view of the rapid elimination of any systemically available Ala-Gln, the risk of systemic drug-drug interactions is considered negligible in this trial.

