6.3 Dosing regimen

MC2-25 cream or MC2-25 vehicle is to be applied twice daily, in the morning and evening, to areas with CKD-aP. The treatment must be applied in a thin even layer to affected areas and rubbed in gently to ensure that the treatment areas are saturated. Treatment of all areas with CKD-aP must be continued until the Week 12 (or EoT) visit. This is also applicable for areas becoming itch-free during trial participation and new areas of CKD-aP identified after the Baseline visit.

The daily dose should not exceed 50 g. Detailed application instructions will be provided in the subject instructions.

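### Protocol 7.12.7 relies on a more than 40-fold safety margin that Section 2.3, its cited source, never derives and that fails under full absorption

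*Protocol*

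**What the plan says.** Protocol 7.12.7 (Trial medication overdose) defines an overdose as any dose above the highest under investigation. It asks for AE reporting when the investigator judges the overdose clinically significant. It then opens a sentence with "In view of the >40-fold systemic safety margin (see Section 2.3" and concludes that a dose several times the highest one studied need not count as clinically significant.

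Protocol 2.3 (Benefit-risk assessment) is the cited source. Its reference is the parenteral Ala-Gln product, "approved for IV human use at doses up to 0.5 g per kg body weight per day". Its exposure input is "In the present trial a maximum of 50 g MC2-25 cream 3% (w/w) will be used per day", which agrees with 6.3 ("The daily dose should not exceed 50 g"). It derives four margins:

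- All applied Ala-Gln absorbed: "This corresponds to ~0.02 g Ala-Gln/kg/day (1.5 g Ala-Gln per day in a 70-kg adult) and a resulting safety margin of 25".
- Less than 1% absorbed: "This corresponds to 0.0002 g Ala-Gln/kg/day and a resulting systemic safety margin of 2500".
- Skin barrier as impaired as in atopic dermatitis, permeation 2.5 times higher: "then the resulting systemic safety margin would be 10 or 1000", for full and under-1% absorption respectively.

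**The concern.** A cross-reference for a safety figure should lead to that figure, and this one does not. The number also does work in the text: it is the stated reason for the remark about doses several times the maximum, in an operational section that investigators consult when an overdose occurs. According to 2.3 this is the first clinical trial of the cream and no clinical data exist, so a site has only the protocol's own reasoning to check the figure against. If the bound fails in some of the scenarios it claims to summarise, the reader of 7.12.7 is given a more favourable picture than 2.3 supports, with no sign that it depends on an absorption assumption.

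**Working it through.** **Inputs (all Protocol 2.3).** Reference IV dose 0.5 g/kg/day; 50 g of cream per day at 3%; body weight 70 kg; absorbed fraction 100% or 1%; permeation multiplier 1 or 2.5.

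**Formula.** Margin = reference dose / (daily Ala-Gln per kg × absorbed fraction × permeation multiplier).

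**Daily Ala-Gln.** 50 × 0.03 = 1.5 g; 1.5/70 = 0.0214 g/kg/day, which 2.3 rounds to about 0.02.

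**Reproducing 2.3, then comparing with 40.**

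| Scenario | Margin from 0.02 g/kg/day | Stated in 2.3 | Unrounded | Above 40? |
|---|---|---|---|---|
| All absorbed | 0.5/0.02 = 25 | 25 | 23.3 | No |
| 1% absorbed | 0.5/0.0002 = 2500 | 2500 | 2333 | Yes |
| All absorbed, 2.5-fold | 25/2.5 = 10 | 10 | 9.3 | No |
| 1% absorbed, 2.5-fold | 2500/2.5 = 1000 | 1000 | 933 | Yes |

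Section 2.3 reproduces from its own rounded exposure. None of its scenarios gives 40.

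**Looking for a source of 40.**

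- Using the 1.6 g/kg/day IV dosage from the pregnancy entry in Table 1 as reference: 1.6/0.02 = 80, and 80/2.5 = 32.
- One 25 g application per day instead of two: 0.5/(25 × 0.03/70) = 46.7. This does not match the stated 50 g daily maximum.
- A margin of exactly 40 at 1.5 g/day needs a body weight of 40 × 1.5/0.5 = 120 kg; 2.3 uses 70 kg.
- A margin of exactly 40 at 70 kg without the multiplier needs an absorbed fraction of 25/40 = 62.5% (23.3/40 = 58% unrounded); 2.3 states no such fraction.

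The origin of 40 cannot be established from the documents.

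**Size.** Against full absorption: 40/25 = 1.6. Because 7.12.7 states a lower bound, the gap is at least this.

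**What is left after an overdose (illustration).** The protocol does not say how many multiples it has in mind, so 3 to 10 is assumed here. A margin of 40 leaves 40/3 = 13.3 down to 40/10 = 4. A margin of 25 leaves 25/3 = 8.3 down to 25/10 = 2.5. This is arithmetic on the stated margins, not a view on which excess dose matters clinically.

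**The case against.** The best defence is that 7.12.7 gives a lower bound, so the absence of the exact number 40 from 2.3 does not refute it. The bound is true of 1000 and 2500, and those rest on the protocol's in vitro skin penetration result; 2.1.2 calls low systemic availability the expected case. This part stands: under the absorption the protocol expects, the margin is far above 40. It does not rescue the sentence, because 7.12.7 names no absorption assumption and cites the whole of 2.3, where two of the four margins fall below the bound. Nor does the word systemic single out the low-absorption cases, since 2.3 applies it to the 10 as well.

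Three stronger readings are tempting and are not supported:

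- **A 4-fold overstatement (40/10).** The 10 applies a 2.5-fold multiplier to absorption that is already complete, which implies 250% of the dose absorbed. On these inputs the margin cannot fall below the full-absorption figure of 25. The 10 shows that the protocol's own worst case contradicts 7.12.7; it does not measure the gap.
- **That 40 decides whether an event is reported.** In 7.12.7 clinical significance is left to the investigator, no threshold is set at 40, and the sentence is hedged. Sections 7.12.1 and 7.12.9 require AEs and SAEs to be recorded and reported whatever the margin.
- **That 25 should be corrected to 23.** Section 2.3 marks its exposure as approximate, and 0.5/0.02 = 25 is right on that figure. The difference is rounding.

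It is also fair to say that the comparator is an approved maximum IV dose, not a toxic one, so a margin below 40 is not in itself a safety signal.

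**Conclusion.** Wrong as written: an inconsistent safety figure. The unqualified bound in 7.12.7 is not derived in 2.3. Among the scenarios given there, it holds only where under 1% is absorbed, and it exceeds the plain full-absorption margin by at least 1.6-fold. This rests only on the protocol's own inputs and its rounded exposure; the unrounded exposure gives the same conclusion.

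The consequence is limited. The figure informs an investigator's judgement in one section. The documents do not show that any reporting decision would change if 25 replaced 40, or that subjects are at added risk. Sample size, power, error rates and every SAP analysis are untouched. It is still worth correcting because it is a figure the text relies on, in a safety section, and the discrepancy runs in the favourable direction.

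**What to change.** Reconcile 7.12.7 with 2.3 in one of two ways. Either replace the 40-fold figure with the margins that 2.3 derives, each with its absorption assumption, or add to 2.3 the derivation that yields 40, with its inputs. In both cases, check that the remark about doses several times the maximum still follows from the figure then cited. If 2.3 is being edited anyway, a short note that the 10 combines complete absorption with a permeation multiplier would help the reader. The 25 can stay as it is.

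The choice of margin and any overdose rule belong to the sponsor; none is proposed here. The cost is a sentence or two in a protocol amendment. If the margins in 2.3 are adopted with their assumptions, the figure shown to investigators for full absorption becomes less favourable. Nothing in the SAP needs to change.
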